9.3 POPULATIONS FOR ANALYSES

Safety will be evaluated with intention-to-treat analysis comparing IN vs IM routes. All subjects receiving the vaccine will be included in the analysis.

9.3.1 Evaluable for Toxicity

All participants will be evaluable for toxicity from the time of their first treatment with BPL-1357 or placebo.

9.3.2 Evaluable for Objective Response

Not applicable.

9.3.3 Evaluable Non-Target Disease Response

Not applicable.

9.4 STATISTICAL ANALYSES

9.4.1 General Approach

AE's and SAE's will be tabulated by severity and by group. Tests of proportions with no continuity correction will be used to test for differences between groups. Confidence intervals around the difference in proportions will be calculated. Antibodies will be compared using t-tests. Antibody data may be transformed by using log transformation to stabilize the variance if the data are skewed.

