6.3 MEASURES TO MINIMIZE BIAS: RANDOMIZATION AND BLINDING

6.3.1 Randomization

Participants will be randomized at enrollment in a 1:1:1 ratio to treatment groups A, B, and C. Randomization will occur using computer-generated randomization codes. This code will be sent to the pharmacy where the unblinded pharmacist will have the key and prepare the appropriate agent for administration. The randomization code list will be maintained by the Investigational Drug Management Research Section (IDMRS) in the electronic Investigational Drug Management System (IDMS).

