9.2 SAMPLE SIZE DETERMINATION

There will be 15 participants in each treatment group. The study will have adequate power to observe safety signals as defined by the 2 pausing criteria.

 A subject experiences an SAE that is unexpected (per the investigator's brochure or product label) and possibly, probably, or definitely related to a study agent or route of administration;

• A subject experiences two grade 3 or greater AEs that are unexpected (per the investigator's brochure or product label) and possibly, probably, or definitely related to a study agent or route of administration.

Table 7 gives the probability of meeting either criteria in just one arm under various true rates. The table shows that if the true rate in a single vaccine arm is 15% there would be a high probability of detecting the safety signal (power of 0.913). If we meet pausing criteria in both arms, then we also meet halting criteria for study.

Table 8. Probability of meeting pausing criteria

True rate of pausing	Probability of pausing
criteria 1 or 2 (%)	(≥ 1/15)
5%	0.537
10%	0.794
15%	0.913

We will also compare AE rates for the combined vaccine arms to the placebo arm at V_2D28 . We will use a 1-sided .05 level test for the comparison of proportions. With this test we will have 80% power if the true rate in the placebo arm is 5% and the true rate in the vaccine arms is 36%. We will also have 80% power if the true rate in the placebo arm is 10% and the true rate in the vaccine arms is 44%. (This calculation was performed using the SWOG statistical tool website with no continuity correction).

For the safety secondary objective we will compares AE rates in a similar manner but at the end of study, V_2D182 . For the immunogenicity secondary objective, we will compare antibodies against H1, H3, H5, H7, N1, N3, N8, and N9 from both blood and mucosal samples between all 3 arms at V_2D28 . With 15 participants in each arm there will be power of 0.82 to detect an effective size of 1.25 (the effective size is the mean/std) using a two-sided 0.05/3=.0167 level t-test. The level of the test has been adjusted to control for the 3 comparisons between all groups. A similar analysis will be performed at other timepoints for one of the exploratory objectives.

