9.4.2 Analysis of the Primary Endpoints

If 1 or more related SAE's are observed in an arm, the primary safety endpoint for that arm will have been met. For the AE safety endpoints, summary statistics will be provided for unexpected safety events. Unexpected safety events will be summarized by treatment group, as well as by individual AE and grouped by type of event. Tests of proportions will be used to compare rates between groups. 90% confidence intervals will be calculated for safety endpoints. This will be done at V_2D28 for the primary endpoint, but a similar analysis will be done for the secondary safety endpoint at V_2D182 .

Two-sided t-tests will be used to compare antibody endpoints at V_2D28 for the secondary objective. All three arms will be compared to each other. A 0.05/3=0.0167 significance level will be used to adjust for the 3 group comparisons. Confidence intervals around group differences will be calculated using the significance level adjusting for the 3 comparisons (each confidence interval will be at the 1-0.0167=0.983 level). Antibody data maybe transformed by using the log10 transformation to stabilize the variance if the data are skewed.

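### The pairwise antibody t-tests name no variance estimator; stating Welch in sections 9.2, 9.4.1 and 9.4.2 would secure the 0.0167 level, with planning power of about 0.80 rather than 0.82

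*Combined protocol and SAP*

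**What the plan says.** The immunogenicity objective is secondary. Section 9.4.1 gives the method: "Antibodies will be compared using t-tests". Section 9.4.2 has all three arms compared with each other and sets the level: "A 0.05/3=0.0167 significance level will be used to adjust for the 3 group comparisons". The intervals follow the same adjustment: "Confidence intervals around group differences will be calculated using the significance level adjusting for the 3 comparisons", that is, 98.3% each.

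Section 9.2 gives the planning figure: "With 15 participants in each arm there will be power of 0.82 to detect an effective size of 1.25", "using a two-sided 0.05/3=.0167 level t-test". It defines the effect size in terms of one SD ("the effective size is the mean/std") and gives no SD by arm. Sizes are equal by design: "There will be 15 participants in each treatment group".

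Both 9.4.1 and 9.4.2 allow a log transformation to steady the variance. It is optional, and its trigger is skewness, not a difference in spread between arms. Nothing is said about pooling, or about what happens if the arms have different variances.

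**The concern.** A t-test for three pairs of arms can be run with an SD pooled over the two arms compared, an SD pooled over all three arms, or separate variances (Welch). The three agree when spreads are equal and diverge when they are not.

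Unequal spread is plausible here for some antigens. The vaccine components are avian viruses, and section 2.2 notes that most people lack protective immunity to novel influenza A viruses. For such antigens the placebo arm may vary little while the vaccine arms vary more. Under three-arm pooling, a small placebo SD would shrink the standard error for IM versus IN, to which the placebo arm contributes no information. Under two-arm pooling, vaccine versus placebo would use too many degrees of freedom, and a wrong standard error once arm sizes differ.

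At stake are the stated level and coverage of the secondary immunogenicity comparisons, including the route contrast. The choice would otherwise remain open until the data are in hand.

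**Working it through.** **Inputs from the documents.** n = 15 per arm; effect size 1.25; two-sided level 0.05/3 = 0.0167 (section 9.2); 98.3% intervals (section 9.4.2).

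**Input assumed.** r = placebo SD / vaccine SD. The documents do not give it, so the range 0.75 to 0.2 is shown, with both vaccine SDs set to 1.

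**1. The plan's power figure.** Taking the effect size as the mean difference divided by a common SD, the noncentrality is 1.25 × √(15/2) = 3.423.

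| Test | df | Critical value | Power |
|---|---|---|---|
| SD pooled over two arms | 28 | 2.546 | 0.803 |
| SD pooled over three arms | 42 | 2.494 | 0.819 |
| Welch, equal SDs (simulated) | – | – | about 0.80 |

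The stated 0.82 matches the three-arm figure to two decimals. An ordinary two-sample t-test gives 0.80.

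**2. Why the estimator matters (r = 0.2).**
- *Three-arm pooling.* The expected pooled variance is (1 + 1 + 0.04)/3 = 0.68. For IM versus IN the correct value is 1, so the standard error is √0.68 = 0.82 of what it should be. For vaccine versus placebo the correct average is (1 + 0.04)/2 = 0.52, so the standard error is too large by √(0.68/0.52) = 1.14.
- *Two-arm pooling, 15 v 15.* The variance of the difference is right on average: 0.52 × 2/15 = 0.0693 = (1 + 0.04)/15. The test uses 28 df, though, where the Satterthwaite value is 14 × 1.04²/(1 + 0.04²) = 15.1.
- *Two-arm pooling, 12 vaccine v 15 placebo.* The pooled variance is (11 × 1 + 14 × 0.04)/25 = 0.4624, giving 0.4624 × (1/12 + 1/15) = 0.0694. The true variance is 1/12 + 0.04/15 = 0.0860. The standard error is √(0.0694/0.0860) = 0.90 of what it should be.

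**3. Actual error rates, nominal 1.67%.** Simulated normal data with equal means. Separate runs agree to within about 0.1 point; where they differ, both values are shown.

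| Comparison and estimator | r = 0.75 | r = 0.5 | r = 0.2 |
|---|---|---|---|
| IM v IN, two-arm pooled, 15 v 15 | 1.7% | 1.7% | 1.7% |
| Vaccine v placebo, two-arm pooled, 15 v 15 | 1.7% | 1.8-1.9% | 2.2-2.3% |
| Vaccine v placebo, two-arm pooled, 12 v 15 | – | 2.7% | 4.0% |
| IM v IN, three-arm pooled, 15 per arm | 2.6-2.7% | 3.7-3.8% | 4.9-5.0% |
| Vaccine v placebo, three-arm pooled, 15 per arm | 1.3% | 1.0% | 0.8% |

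With 13 v 15 and r = 0.2, two-arm pooling gives 3.2%. Welch stayed between 1.6% and 1.75% in every scenario.

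Coverage is one minus these rates. At r = 0.2 a nominal 98.3% interval covers about 95% for IM versus IN under three-arm pooling, and about 96% for vaccine versus placebo under two-arm pooling with 12 v 15.

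**The case against.** The strongest reply is that the plan says only that t-tests will be used, and Welch is a t-test. That is right: a reader might infer that the plan assumes a common SD, but no section says so. The gap is one of silence.

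A reader might also infer from 0.82 that the route contrast will use an SD pooled over three arms and so run at about 5%. The documents do not support this. The gap from 0.803 to 0.819 is 1.6 points, and small changes in the inputs close it: a two-arm test with the level entered as 0.02 gives 0.824, and one with effect size 1.27 gives 0.817. Section 9.4.2 describes pairwise two-sided tests with no common error term, and section 9.4.6 names analysis of variance with Tukey where it is wanted, for influenza rates. Under ordinary two-sample tests the placebo data do not enter IM versus IN, which keeps 1.67%.

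A third inference would be that placebo titres sit at the assay floor for every antigen. No placebo titre, SD or detection limit is given. Section 2.2 describes annual H1N1 and H3N2 epidemics, and section 5.1 admits people vaccinated against influenza more than 8 weeks earlier, so a floor is doubtful for H1, H3 and N1.

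Finally, with equal means in all arms, familywise error stays near 5% (at most 5.3% under two-arm and 5.7% under three-arm pooling). That gives less comfort if both vaccine arms differ from placebo: IM versus IN may then be the only true null left, and its own rate is what counts.

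What survives is that the estimator is unstated, the log transformation need not equalise spreads, and unequal arms are possible. Section 8.4.4.2 makes replacement optional and limits it to losses before V2D7, while the endpoint is at V2D28.

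**Conclusion.** The point holds as a minor one. The plan leaves the variance estimator open, and the permitted readings give different error rates if spreads differ. On the usual two-sample reading the effect is small: IM versus IN is unaffected, and vaccine versus placebo runs at 1.7-2.3% with 15 v 15, rising to about 4% only with 12 v 15 and a placebo SD one fifth of the vaccine SD. Three-arm pooling would put IM versus IN at about 2.7-5.0%; the upper end needs a placebo SD of about a quarter of the vaccine SD or less.

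These rates rest on the assumed SD ratio, on normal data and on equal vaccine SDs. Skewness and censoring at a detection limit were not part of the rates shown. Independently of any SD ratio, 0.82 is slightly high for a two-sample t-test with 15 per arm, which gives 0.803.

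**What to change.** In sections 9.2, 9.4.1 and 9.4.2, state that each pairwise antibody comparison and its 98.3% confidence interval uses the Welch (unequal-variance) t-test with the variances of the two arms compared, and that no SD is pooled across arms. In section 9.2, restate the planning power as about 0.80 at an effect size of 1.25.

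The cost is one sentence and about two points of stated power (0.82 to 0.80). Sample size, level and the set of comparisons do not change.

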9.4.2 Analysis of the Primary Endpoints

If 1 or more related SAE's are observed in an arm, the primary safety endpoint for that arm will have been met. For the AE safety endpoints, summary statistics will be provided for unexpected safety events. Unexpected safety events will be summarized by treatment group, as well as by individual AE and grouped by type of event. Tests of proportions will be used to compare rates between groups. 90% confidence intervals will be calculated for safety endpoints. This will be done at V_2D28 for the primary endpoint, but a similar analysis will be done for the secondary safety endpoint at V_2D182 .

Two-sided t-tests will be used to compare antibody endpoints at V_2D28 for the secondary objective. All three arms will be compared to each other. A 0.05/3=0.0167 significance level will be used to adjust for the 3 group comparisons. Confidence intervals around group differences will be calculated using the significance level adjusting for the 3 comparisons (each confidence interval will be at the 1-0.0167=0.983 level). Antibody data maybe transformed by using the log10 transformation to stabilize the variance if the data are skewed.

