1 PROTOCOL SUMMARY

1.1 SYNOPSIS

Title:

Randomized, Double-Blinded, Placebo-Controlled, Phase 1 Study of the Safety and Immunogenicity of BPL-1357, a BPL-Inactivated, Whole-Virus, Universal Influenza Vaccine

Study Description:

This is a randomized, double-blinded, placebo-controlled, single-center, phase 1 clinical trial of β -propiolactone (BPL)-inactivated quadruple influenza virus cocktail vaccine (BPL-1357) administered intramuscularly (IM) or intranasally (IN) in 2 doses 28 days apart. Participants will be randomized to one of three groups for treatment assignment. The primary hypothesis is that IN and IM BPL-1357 will be well tolerated.

Objectives:

Primary Objective:

1. To assess the safety of BPL-1357 given IM or IN, compared to placebo.

Secondary Objective:

- 1. To further assess the safety of BPL-1357 given IM or IN, compared to placebo.
- 2. To assess the immunogenicity of BPL-1357 given IM or IN, compared to placebo.

Tertiary Objective:

- 1. To characterize the systemic and mucosal humoral immune responses induced by BPL-1357 given IM or IN, compared to placebo.
- 2. To further characterize the immune response induced by BPL-1357 given IM or IN through variable, diversity, and joining (VDJ) gene repertoire analysis, cytokine analysis, cytometry, transcriptomics, and assessment of T-cell responses.
- 3. To assess the rates of influenza disease among groups given IM or IN BPL-1357 compared to placebo.

Endpoints:

Primary Endpoints:

- 1. Type and severity (by grading) of adverse events (AEs) through vaccine 2 (V₂) day 28 (D28) [28 days after vaccine dose 2].
- 2. Type of serious adverse events (SAEs) through V₂D28 [28 days after vaccine dose 2].

Secondary Endpoints:

- 1. Safety
 - a. Type and severity (by grading) of AEs through V₂D182 [182 days after vaccine dose 2].

- b. Type of SAEs through V₂D182 [182 days after vaccine dose 2].
- 2. Immunogenicity
 - a. Antibodies against H1, H3, H5, and H7 head and stalk as measured by hemagglutination inhibition (HAI) or enzyme-linked immunosorbent assay (ELISA) from blood and mucosal samples at V₂D28.
 - b. Antibodies against N1, N3, N8, and N9 as measured by neuraminidase inhibition (NAI) or ELISA from blood and mucosal samples at V₂D28.

Tertiary Endpoints:

- 1. Additional antibody titer characterization via:
 - a. Antibodies against H1, H3, H5, and H7 head and stalk as measured by HAI or ELISA from blood and mucosal samples at V₁D7, V₁D14, V₁D28, V₂D7, V₂D14, V₂D56, and V₂D182.

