3 OBJECTIVES AND ENDPOINTS

Table 2: Objectives and Endpoints

OBJECTIVES	ENDPOINTS	JUSTIFICATION FOR ENDPOINTS	
Primary			
To assess the safety of BPL-1357 given IM or IN, compared to placebo.	 a. Type and severity (by grading) of AEs through day V₂D28. b. Type of SAEs through day V₂D28. 	The standard way to determine safety is to evaluate AE incidence and severity.	
Secondary			
 To further assess the safety of BPL-1357 given IM or IN, compared to placebo. To assess the immunogenicity of BPL- 	Type and severity (by grading) of AEs through day V ₂ D182.	Analysis of antibody titers will enhance our understanding of the immune response to BPL-1357.	

OBJECTIVES	ENDPOINTS	JUSTIFICATION FOR ENDPOINTS
1357 given IM or IN, compared to placebo.	 b. Type of SAEs through day V₂D182. 2. Immunogenicity c. Antibodies against H1, H3, H5, and H7 head and stalk as measured by HAI or ELISA from blood and mucosal samples at V₂D28. d. Antibodies against N1, N3, N8, and N9 as measured by NAI or ELISA from blood and mucosal 	
	samples at V ₂ D28.	
Tertiary/Exploratory		
 To characterize the systemic and mucosal immune responses induced by BPL-1357 given IM or IN, compared to placebo. To further characterize the immune response induced by BPL-1357 given IM or IN through variable, diversity, and joining (VDJ) gene repertoire analysis, cytokine analysis, cytometry, transcriptomics, and assessment of T-cell responses. To assess the rates of influenza disease among groups given IM or IN BPL-1357 compared to placebo. 	 Antibodies against H1, H3, H5, and H7 head and stalk as measured by HAI or ELISA from blood and mucosal samples at V₁D7, V₁D14, V₁D28, V₂D7, V₂D14, V₂D56, and V₂D182. Antibodies against N1, N3, N8, and N9 as measured by NAI or ELISA from blood and mucosal samples at V₁D7, V₁D14, V₁D28, V₂D7, V₂D14, V₂D56, and V₂D182. VDJ gene repertoire analysis. Cytokine analysis. Flow cytometric phenotyping of lymphocytes. Transcriptomic gene expression. T-cell responses. 	Additional analysis of antibody titers will further enhance our understanding of the immune response to BPL-1357. VDJ gene repertoire analysis, cytokine analysis, flow cytometry, transcriptomic analysis, and analysis of T-cell activity may help identify other possible correlates of protection for influenza after vaccination, such as innate and other cellular responses. Rates of influenza disease among groups may provide additional data regarding vaccine-associated immunity

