 - O Hospitalization due to a condition that has not worsened and that pre-dates study participation (e.g., elective correction of an unchanged baseline skin lesion), or due to social circumstance (e.g., prolonged stay to arrange aftercare), or that is planned/required "per protocol" AND that proceeds without prolongation or complication, is NOT considered an SAE by this criterion.
- is, or results in, a persistent or significant incapacity or substantial disruption of the ability to conduct normal life functions.
- is a congenital anomaly/birth defect/miscarriage/stillbirth.

NOTE: This definition is more inclusive than some commonly published definitions. It includes an affected conceptus/neonate whose:

- biological mother was exposed to a study agent at any point from conception through the end of the pregnancy, AND/OR, if breastfeeding, the 30-day neonatal period; or
- o biological father was exposed to a study agent at any point during the 90 days prior to conception.

This is separate from, and in addition to, general reporting of pregnancy in a study participant or female partner of a male participant (see section 8.4.3.3.4 below).

• is a medically important event.

NOTE: Medical and scientific judgment should be exercised. Events that significantly jeopardize the subject and/or require intervention to prevent one of the SAE outcomes listed above are generally considered medically important, and are thus SAEs.

Unexpected Adverse Event: An AE is unexpected if it is not listed in the investigator's brochure or package insert (for marketed products) at the frequency, AND specificity, AND severity that has been observed.

NOTE:

- Such events should also be evaluated for possible reporting as unanticipated problems (UPs) (see section 8.4.3.3.3 below).
- Unexpected, as used in this definition, also refers to AEs or SARs that are mentioned in the investigator's brochure as occurring with a class of drugs/biologics, or as anticipated from the pharmacological properties of the study agent but are not specifically mentioned as occurring with the particular study agent under investigation.

Serious and Unexpected Suspected Adverse Reaction (SUSAR): A SUSAR is an SAR (defined above) that is both serious and unexpected.

Unanticipated Problem: A UP is any incident, experience, or outcome that meets all the following criteria:

- 1. Unexpected (in terms of nature, severity, or frequency) given

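### Section 9.4.2 summarises unexpected events although the primary endpoint is type and severity of all AEs, and it does not say which events its tests and 90% intervals cover

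*Combined protocol and SAP*

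**What the plan says.** **Endpoint.** The synopsis (1.1) defines the first primary endpoint as "Type and severity (by grading) of adverse events (AEs) through vaccine 2" day 28. Table 2 in section 3 repeats it and gives the reason: "The standard way to determine safety is to evaluate AE incidence and severity". Neither place restricts the endpoint by expectedness.

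**Primary analysis.** Section 9.4.2 says "For the AE safety endpoints, summary statistics will be provided for unexpected safety events", and then "Unexpected safety events will be summarized by treatment group, as well as by individual AE and grouped by type of event". Grade is not mentioned. Two further sentences follow: "Tests of proportions will be used to compare rates between groups" and "90% confidence intervals will be calculated for safety endpoints". Neither names the events counted.

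**Other sections.** Section 9.4.1 says AEs and SAEs will be "tabulated by severity and by group", with tests of proportions and confidence intervals for differences. Section 9.2 compares AE rates at V2D28 between the combined vaccine arms and placebo, at a one-sided 0.05 level. Neither section filters by expectedness.

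**Definition.** Section 8.4.1 begins "An AE is unexpected if it is not listed in the" and refers to the investigator's brochure or package insert, at the frequency, specificity and severity observed. Events known for the class, but not specifically mentioned for this agent, also count as unexpected.

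**The concern.** The primary hypothesis (9.1) is that the vaccine is well tolerated with only minor side effects. That is judged from how often reactions occur and how severe they are, whether or not they are already listed. Expectedness serves a different purpose. It suits the pausing and halting rules, where the question is whether something new has appeared. As the filter for the primary summary it has three drawbacks:

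- The content of the summary depends on a document outside the protocol, and a brochure revision during the study could change it.
- Severity is half of the endpoint, and 9.4.2 leaves it out.
- With 9.4.2 pointing to one event set and 9.2 and 9.4.1 to another, an analyst could choose between them after seeing the data.

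The choice also decides whether the power statement in 9.2 describes the test that will be run.

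**Working it through.** **1. The sections side by side**

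| Place | Events | Severity | Comparison |
|---|---|---|---|
| 1.1 and Table 2 (endpoint) | all AEs | yes | vaccine against placebo (objective) |
| 9.4.2 (primary analysis) | unexpected events | not mentioned | tests and 90% intervals, event set not named |
| 9.4.1 (general approach) | all AEs and SAEs | yes | tests and intervals for differences |
| 9.2 (V2D28 comparison) | AE rates, no filter | not mentioned | combined vaccine arms against placebo |

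Section 9.4.2 is the only one of the four that filters by expectedness, and it is the one headed as the primary analysis.

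**2. The plan's power figure**

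Inputs from 9.2: 15 per arm, hence 30 vaccine against 15 placebo; one-sided 0.05; no continuity correction; 5% against 36% and 10% against 44%.

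For the pooled z-test, power = Φ[(p2 − p1 − 1.645·SE0) / SE1], where
- p̄ = (15·p1 + 30·p2)/45
- SE0 = √[p̄(1 − p̄)(1/15 + 1/30)]
- SE1 = √[p1(1 − p1)/15 + p2(1 − p2)/30]

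*5% against 36%:* p̄ = (0.75 + 10.8)/45 = 0.2567; SE0 = 0.1381; SE1 = 0.1041; (0.31 − 1.645 × 0.1381)/0.1041 = 0.795; power 0.787.

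*10% against 44%:* p̄ = (1.5 + 13.2)/45 = 0.3267; SE0 = 0.1483; SE1 = 0.1192; (0.34 − 1.645 × 0.1483)/0.1192 = 0.806; power 0.790.

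Summing binomial probabilities over all outcomes that the same test rejects gives exact power of 0.813 and 0.798. The stated 80% reproduces.

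**3. Does that 80% carry over to either event set?**

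The documents give no rates by event set, so the rates below are assumptions. Exact power, same test:

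| Event set | Placebo | Vaccine | Power |
|---|---|---|---|
| Unexpected AEs only | 2% | 5% | 0.01 |
| Unexpected AEs only | 5% | 10% | 0.08 |
| Unexpected AEs only | 2% | 10% | 0.13 |
| Any AE | 50% | 85% | about 0.80 |
| Any AE | 60% | 91% | about 0.80 |
| Any AE | 80% | 99.5% | about 0.80 |

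If unexpected events are rare, the test has almost no power. If the tested variable is any AE and that is common on placebo, the vaccine rate must be very high to reach 80%. A placebo rate above 5-10% is possible, because every placebo participant receives both an injection and a nasal dose and 2.3.1.2 says saline itself can cause local symptoms. No frequencies are given there, so this does not show that the planning rates are wrong.

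**The case against.** A reader might infer from 9.4.2 that expected vaccine reactions drop out of the trial's safety result. The documents do not support that. Section 9.4.1 is the general approach to all the analyses; it tabulates every AE by grade and arm and then provides tests between groups. Section 9.2 separately commits to an unfiltered comparison of AE rates at the primary time point. The daily surveys are reviewed for AEs under 8.3, so what they record can reach the 9.4.1 tabulation. It also goes too far to say that severity enters no between-group comparison: the omission is specific to 9.4.2.

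Nor can a reader conclude that common reactions will be filtered out. The investigator's brochure is not among the documents. Section 2.3.1.1 says the risks of this agent are not well known, and under 8.4.1 a reaction known only for the class still counts as unexpected. The filter might remove little or nothing.

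These objections limit the consequence. They do not resolve the conflict. Nothing in the plan ranks 9.4.1 above 9.4.2 for the primary endpoint, and an analyst would normally follow the more specific section. That the filter's effect cannot be read from the protocol is itself part of the problem.

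**Conclusion.** The point holds as a conflict between sections. Section 9.4.2 does not match the primary endpoint, or 9.2 and 9.4.1, on which events form the primary summary; it omits severity; and it leaves the events for its tests and 90% intervals undefined. The primary summary therefore depends on brochure listing and may omit listed reactions relevant to tolerability. All AEs remain tabulated by severity and group under 9.4.1.

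The size of any omission cannot be stated without the brochure. The 80% power is correct for the rates in 9.2 (exact 0.81 and 0.80) and applies only to an event set with rates near those. The other power figures illustrate the dependence under assumed rates and are not predictions. Sample size is unaffected.

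**What to change.** 1. In 9.4.2, replace unexpected safety events with all AEs, from the surveys and unsolicited. Summarise them by type and by maximum grade per participant, by treatment group. Report unexpected and related events as additional subsets.
2. Before unblinding, name one event set for the 9.2 comparison and for the 90% intervals. The choice belongs to the sponsor.
3. Confirm that the 5-10% placebo planning rates fit that event set. If they do not, restate the power in 9.2 for rates that do.

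The cost is wording in 9.2 and 9.4.2 and a few tables. The data are already to be collected, and the number of participants stays the same.

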2.3.1.2 Risks of Placebo Administration

IM Placebo Administration: IM injection of saline can cause muscle soreness and injection-site pain, redness, swelling, and bruising.

IN Placebo Administration: IN administration of normal saline can cause sneezing, coughing, nose irritation, abnormal taste, and nose bleeding.

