6.1.2 Dosing and Administration

A single study agent dose of 1 mL will be used either IM or given in two doses of 0.5 mL IN in each nare. Participants will be randomized to receive IM and IN doses of study agents twice 28 days apart as follows:

- Group A: IM BPL-1357 and IN placebo.
- Group B: IM placebo and IN BPL-1357.
- Group C: IM and IN placebo.

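### No stated comparison sets a site's 15 vaccine recipients against all 30 participants who received saline at that site

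*Combined protocol and SAP*

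**What the plan says.** **Design.** Section 6.1.2 is a double dummy. Group A receives IM vaccine and IN placebo, Group C receives placebo by both routes, and the middle arm is "Group B: IM placebo and IN BPL-1357". Section 9.2 sets the size: "There will be 15 participants in each treatment group". Section 2.3.1.2 lists local effects of saline at each site; for the muscle, "IM injection of saline can cause muscle soreness and injection-site pain, redness, swelling, and bruising".

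**Comparisons of adverse events.**

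- Section 9.2: combined vaccine arms against the placebo arm at V2D28. "We will use a 1-sided .05 level test for the comparison of proportions". This is the only between-arm adverse-event comparison with a stated power: 80% at 5% vs 36% and at 10% vs 44%.
- Section 9.3: safety compared between the IN and IM routes.
- Section 9.4.1: events tabulated by severity and by group, with uncorrected tests of proportions between groups.
- Section 9.4.2: summaries of unexpected events by treatment group, by individual event and by type, followed by "Tests of proportions will be used to compare rates between groups" and 90% confidence intervals.

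**Data.** Table 1 (note b) and section 8.3 collect local and general symptoms daily for 7 days after each dose. No site-specific endpoint, site-level analysis or expected site-reaction rate is given.

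**The concern.** For an injection-site reaction, the exposed participants are those in A, and both B and C had saline in the muscle. For a reaction specific to the nose, the exposed participants are those in B, and both A and C had saline there. The double dummy therefore supplies 30 randomised, blinded saline recipients per site, but each stated comparison uses at most 15 of them as controls:

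- A vs C, or B vs C, leaves out the other vaccine arm's saline recipients.
- A vs B uses those recipients and leaves out C.
- A+B vs C puts them on the vaccine side.

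The primary objective is safety by IM or IN compared with placebo, so local tolerability by route is central to the trial. What is at stake is precision and power for moderate local effects, not the validity of the by-arm tables.

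**Working it through.** **Inputs.** 15 per arm; one-sided .05; no continuity correction; planning rates "if the true rate in the placebo arm is 5% and the true rate in the vaccine arms is 36" (per cent) and "if the true rate in the placebo arm is 10% and the true rate in the vaccine arms is 44" (per cent), all from section 9.2. Arms by site come from section 6.1.2. Using these adverse-event rates for site reactions is an assumption.

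**Step 1: reproduce the plan's power.** With v = vaccine and c = control:

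- s0 = √[p̄(1−p̄)(1/nv + 1/nc)], where p̄ is the pooled rate
- s1 = √[pv(1−pv)/nv + pc(1−pc)/nc]
- power = Φ[(pv − pc − 1.645·s0)/s1]

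For 30 vs 15:

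- 36% vs 5%: p̄ = (30×0.36 + 15×0.05)/45 = 0.257, s0 = 0.138, s1 = 0.104, power 0.787.
- 44% vs 10%: p̄ = 0.327, s0 = 0.148, s1 = 0.119, power 0.790.

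Both are close to the stated 80%. A two-sided test would give 0.647 and 0.660, so one-sided is the version the plan used.

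**Step 2: recipients per site.** Muscle: vaccine A = 15, saline B + C = 15 + 15 = 30. Nose: vaccine B = 15, saline A + C = 30.

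**Step 3: one vaccine arm against 15 or 30 saline controls.** The same approximation gives 0.690 to 0.827 (36% vs 5%, gain 13.7 points) and 0.688 to 0.819 (44% vs 10%, gain 13.1 points).

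Exact power sums Bin(a; nc, pc)·Bin(b; nv, pv) over all outcomes in which the uncorrected z exceeds 1.645:

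| Vaccine vs saline rate | 15 vs 15 | 15 vs 30 | Gain (points) |
|---|---|---|---|
| 36% vs 5% (plan) | 0.754 | 0.866 | 11.2 |
| 44% vs 10% (plan) | 0.738 | 0.833 | 9.5 |
| 20% vs 5% (assumed) | 0.347 | 0.498 | 15.1 |
| 50% vs 20% (assumed) | 0.556 | 0.668 | 11.3 |
| 60% vs 20% (assumed) | 0.753 | 0.859 | 10.7 |
| 60% vs 10% (assumed) | 0.936 | 0.978 | 4.2 |
| 60% vs 5% (assumed) | 0.983 | 0.996 | 1.3 |
| 70% vs 10% (assumed) | 0.983 | 0.997 | 1.4 |

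The gain nearly vanishes when a high vaccine rate meets a low saline rate, because 15 vs 15 already detects it. It stays near 11 points at 60% vs 20%.

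**Step 4: test size.** Exact size of the uncorrected test, 15 vs 15 then 15 vs 30, at common rates:

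- 5%: 1.7% then 5.0%
- 10%: 4.3% then 6.1%
- 20%: 5.8% then 5.4%

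At low common rates part of the gain is therefore a looser test. With a mid-p Fisher test, whose size for 15 vs 30 is 1.1% to 4.5% at common rates of 5% to 30%, power goes from 0.681 to 0.821 (36% vs 5%), 0.678 to 0.808 (44% vs 10%) and 0.520 to 0.636 (50% vs 20%). Those gains are 14.0, 13.0 and 11.6 points. The mid-p test is also smaller with 15 controls, so it does not equalise size fully.

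**Step 5: A+B vs C for a reaction confined to one site.** The vaccine-side rate is diluted to (15×36% + 15×5%)/30 = 20.5%, or (15×44% + 15×10%)/30 = 27%. Exact power, enumerating the three arms separately, is 0.412 and 0.359. Against 0.866 and 0.833 for 15 vs 30, that is 45.4 and 47.4 points lower.

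**The case against.** The strongest case on the other side has five parts.

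1. **The plan may not test site reactions at all.** The quoted sentence in 9.4.2 follows two sentences about unexpected events, while injection-site pain, redness and swelling, nose irritation, nosebleed and abnormal taste are listed as possible risks in 2.3.1.1. This stands in part. Formal testing of these reactions rests on the general rule in 9.4.1. It is also a reason to say explicitly how they will be analysed.
2. **A reader might infer that half the saline recipients go unused.** The documents do not support that. The IN versus IM comparison uses the other vaccine arm's saline recipients, and A+B vs C includes them on the vaccine side. What holds is that no stated comparison uses all 30 as controls.
3. **A reader might infer a fixed loss of 10 to 15 points.** The documents give no site-reaction rate, the planning rates are for adverse events overall, and the exact gain runs from 1.3 to 15.1 points over the rates shown.
4. **By-arm tables are valid and unbiased, and a reader could add B and C by eye.** True. Leaving the pooling to the reader after unblinding is weaker than specifying it beforehand.
5. **Pooling assumes that vaccine at the other site does not change the local reaction.** This stands. A check of 15 vs 15 has low power, so it cannot settle the assumption.

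**Conclusion.** The point holds as a cheap improvement, not as an error in the plan. Each site has 15 vaccine and 30 saline recipients, and no stated comparison sets one against the other in full. At the plan's own planning rates, if they apply to site reactions, using all 30 controls raises exact power by 9.5 to 11.2 points over 15 vs 15. If A+B vs C were the comparison relied on for a one-site reaction, power would be only 0.36 to 0.41.

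The size rests on three assumptions: the borrowed rates, the one-sided uncorrected test, and no cross-site effect. Some of the gain at low rates is a change in test size. Nothing here shows that the by-group analysis is invalid or that the trial is too small for its stated comparison.

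**What to change.** Add to section 9.4.2, beside the by-group tables:

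- A supplementary comparison of solicited injection-site reactions as A (15) vs B+C (30), and of reactions listed only for the nasal route (such as nose irritation, nosebleed and abnormal taste, with the terms named in advance) as B (15) vs A+C (30). Give a 90% confidence interval for each difference.
- A statement that this applies whether or not the event counts as unexpected.
- Systemic events, and events listed for both routes such as runny nose or cough, stay by treatment group.
- The assumption that vaccine at the other site does not alter the local reaction, with A vs C and B vs C shown as a limited, low-powered check.

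The cost is a few sentences and one table, fixed before the unblinding in section 6.3.3. It needs no new participants, data or procedures. The downside is reliance on the no-cross-site assumption, which is why the by-group tables remain.
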